9.0. Criteria for response, overall response and disease control

Response must be evaluated using RECIST ver.1.1. Tumor lesions must be accurately measured in at least one dimension (longest diameter in the plane of measurement is to be recorded) with a minimum size of 10 mm by CT scan (irrespective of scanner type) and magnetic resonance imaging (MRI) (*no less than double the slice thickness and a minimum of 10 mm*), 10 mm caliper measurement by clinical examination (when superficial), and 20 mm by chest X-ray (if clearly defined and surrounded by aerated lung).

Tumor lesions must be accurately measured in at least one dimension of local recurrence and skin metastases if applicable. These will be measured by caliper, and the extent of disease should be recorded on a photograph with a scale marker and injection marker. If these lesions are immeasurable, their extent should also be recorded on a photograph with a scale marker and injection marker to assess the rate of overall response.

9.1. Complete Response (CR): Disappearance of all target and non-target lesions at a minimum of 4 weeks.

9.2. Partial Response (PR): At least a 30% decrease in the sum of the longest diameter of the target lesions at a minimum of 4 weeks, taking as a reference the baseline sum of the longest diameter with target.

9.3. Stable Disease (SD): Neither sufficient shrinkage to qualify for PR nor sufficient increase to qualify for progressive disease (PD), taking as a reference the smallest sum of the longest diameter since the treatment started with target lesions.

9.4. Progressive disease (PD): At least a 20% increase in the sum of diameters of target lesions, taking as reference the smallest sum on study (this includes the baseline sum if that is the smallest on study). In addition to the relative increase of 20%, the sum must also demonstrate an absolute increase of at least 5 mm. (Note: the appearance of one or more new lesions is also considered progression). In the previous phase III melanoma study, PD (defined by modified WHO criteria) prior to response was observed in about 50% of responders, and median time to response was 4.1 months. Thus, for this study purpose, a true PD will be confirmed at the end of cycle 10 (approximately 5 months) as long as patients tolerated the treatment.

9.5. Criteria for Overall Response

Response definition among measurable and non-measurable disease combination. Overall response will be defined as a sum of the 3 response types.

	Non-measurable disease (i.e., bone)	Measurable disease (i.e., lung, liver, lymph nodes)
Type I measurable disease only	None	CR or PR,
Type II non-measurable disease only	CR,	None
Type III Both measurable and non-measurable disease	CR,	CR or PR,

A patient with PD of measurable disease prior to end of cycle 10 would be considered to have overall response if the PD is not confirmed at the end of cycle 10.

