6.5 The end of study

6.5.1. Definition of the end of the study

Previous talimogene laherparepvec single agent study showed that the median time to response was 4.1 months, and 50 % of these responders had progressive disease (PD) (defined by modified WHO criteria) prior to response. In this study talimogene laherparepvec administration will continue for at least 10 cycles (approximately 5 months) unless uncontrolled disease progression is observed. Beyond 10 cycles, progressive disease will be measured based on RECIST ver1.1.

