- c. Survival Follow-Up: approximately every 3 months patient survival information will be followed by chart reviewing, or by phone up to 1 year.
10. Female patients of childbearing potential must have a negative urine or blood pregnancy test no more than 3 days prior to starting study drug.
11. Tumor markers (CA 27.29) will be assessed at baseline, before cycle 5 and every additional 4 cycles of treatment. IgG and IgM will be tested at baseline only
12. Disease assessment will be performed at the end of cycle 4, cycle 8 and cycle 10
13. Breast sonography with axillary assessment if clinically indicated

Abbreviation; HE: hematoxilin and eosin staining, IHC: immunohistochemical staining,: talimogene laherparepvec

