9.6. Criteria for Disease Control

Disease control definition among measurable and non-measurable disease combination

Controlled Disease	Non-measurable disease (i.e., bone)	Measurable disease (i.e., lung, liver, lymph nodes)
Type I measurable disease only	None	CR or PR, or SD \geq 4 months or no true PD (at cycle10)
Type II non-measurable disease only	CR, or SD \geq 4 M	None
Type III Both measurable and non-measurable disease	CR, or SD \geq 4 M	CR or PR, or SD \geq 4 months or no true PD (at cycle10)

A patient with PD of measurable disease prior to end of cycle 10 would be considered to have disease control if the PD is not confirmed at the end of cycle 10.

9.7. Response will not be considered evaluable in the following categories:

9.7.1. Early Deaths: Patients who die within the first 2 weeks of the initiation of drug therapy owing to concurrent disease. These cases will be considered treatment failures in the intent-to-treat analysis.

9.7.2. Lost to Follow-up: Patients for whom there is inadequate information to judge tumor response because of loss of contact with our institution (>2 months after a missed appointment) and with referring physician in spite of repeated attempts to locate them. These cases will be considered treatment failures in the intent-to-treat analysis.

9.7.3. Major Protocol Violation: Patients who significantly deviate from the treatment program by either adding or deleting another agent or another therapeutic maneuver or by modifying substantially the dosage and schedule of the drug under evaluation. Patients who do not fulfill the requirements outlined under Patient Eligibility are also included in this category.

9.8. Down staging is defined as a change in the tumor extent that results in reclassification of the primary tumor and/or regional lymph node metastases into a different (lower) T, N, or M subgroup.

9.9. All subjective toxic effects encountered during the study will be evaluated according to the CTCAE version 4.0. Objective toxic effects will be considered as the maximum numerical deviation from the normal range.

9.10. The survival of patients will be measured from the date of registration.

9.11. Patients will be monitored for 1 year after removal from the study or until death, whichever occurs first. Patients removed from study for unexpected adverse events will be monitored until AE is resolved or stabilized.

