13.0. Statistical consideration

13.1. Statistical design

The primary objective of this phase II trial is to assess the efficacy of talimogene laherparepvec as a single agent in locally recurrent IBC and non-IBC patients. The primary endpoint is the rate of overall response.

The overall response rate is defined as the percentage of CR, PR in overall patients. Patients will be evaluated for disease control at the end of cycle 4 (2 months), cycle 8 (4 months) and cycle 10 (5 months). If patients have measurable disease only and achieve CR or PR, they will be considered Response Type I. If patients have non-measurable disease only, and achieved CR, they will be considered as Response Type II. If patients have both measurable and non-measurable disease and achieve CR or PR at the measurable disease sites, and achieved CR at the non-measurable disease site, they will be considered as Response Type III. If patients have mixed responses such as progression of measurable disease and no progression of non-measurable disease at 5 months or vice versa, they will be considered to have uncontrolled disease. The Overall Response rate will be defined as a sum of the 3 response types.

The trial will be conducted using a two-stage design and the overall response rate will be estimated accordingly. It is assumed that the talimogene laherparepvec single agent will have a response rate of 20%. A response rate of 5% or lower will be considered treatment failure and the regimen will be rejected under this circumstance. 13 patients will be enrolled to the first stage. The study accrual will be delayed until all 13 patients are evaluable for response. A summary report will be submitted to the medical monitor in the IND office. If no patients achieve an overall response to the treatment, the trial will be stopped and the regimen will be declared as ineffective. If there are 1 or more patients achieve an overall response, 22 more patients will be enrolled to the study to reach a total of 35 treated patients. By the end of the study, the new regimen will be rejected if less than or equal to 3/35 patients achieve overall response and will not be considered worthy of further investigation otherwise.

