Secondary objectives includes determining the overall disease control rate, local overall response rate and disease control rate, PFS, and OS in all patients; the local overall response rate and disease control rate, PFS, and OS in patients without distant metastases; and the local overall response rate and disease control rate, PFS, and OS in patients with distant metastases for defining the local efficacy of talimogene laherparepvec injection among breast cancer patients with inoperable local recurrence after surgery. In addition, this includes safety and tolerability of talimogene laherparepvec in these patients. The definition of PFS is time from treatment initiation until disease progression or death and this progression needs to be confirmed after the end of cycle 10. For example, patients who showed progress at 2 months but responded as PR at 5 months, we determine this as PR. In contrast, patients who showed progress at 2 months and was confirmed PD at 5 months, we determine this as PD at 2 months. The definition of OS is time from treatment initiation until any cause of death.

Analysis plan:

By the end of the study, the overall response rate will be estimated with 95% confidence intervals for all evaluable patients and for patients with or without distant metastasis, separately. PFS and OS from registration will also be estimated using Kaplan-Meier method with 95% confidence intervals.

Biomarker endpoints will be measured in tissue and in surrogate blood or plasma before and after the treatment. Correlation between biomarkers from various markers and between tissue and blood/plasma will be assessed by Pearson or Spearman rank correlation coefficients for

continuous biomarkers and by chi-square or Fisher's exact test for discrete covariates. The associations between markers or change in the level of markers and overall response status will first be assessed graphically and then tested using a t-test/analysis of variance or Wilcoxon rank sum test/Kruskal-Wallis test, when appropriate. Repeated measures analysis including mixed effects modeling will be performed to analyze biomarkers change over time. We may also evaluate the association between the changes in the level of marker and the overall response status.

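### The last sentence of section 9.5 lets unconfirmed early progression count as overall response without CR or PR, contradicting the 9.5 table and section 13.1

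*Combined protocol and SAP*

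**What the plan says.** Section 13.1 defines the primary endpoint: "The overall response rate is defined as the percentage of CR, PR in overall patients". The table in 9.5 and the three response types in 13.1 agree. Measurable disease must reach CR or PR, and non-measurable disease must reach CR.

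The sentence under the 9.5 table sets a different rule. A patient with PD of measurable disease before the end of cycle 10 "would be considered to have overall response if the PD is not confirmed at the end of cycle 10". It mentions neither CR nor PR.

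Section 9.6 has the same sentence for the secondary endpoint: such a patient "would be considered to have disease control if the PD is not confirmed at the end of cycle 10". It fits there, because the 9.6 table lists absence of true PD at cycle 10 as one form of control for measurable disease. The 9.5 table has no such category.

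Three other places bear on the meaning:

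- Section 9.4 notes that about half of the responders in the melanoma phase III study had PD first, and states that "a true PD will be confirmed at the end of cycle 10 (approximately 5 months) as long as patients tolerated the treatment".
- The PFS example in 13.1 reads: "patients who showed progress at 2 months but responded as PR at 5 months, we determine this as PR".
- Note 12 of the study calendar (8.3) fixes the assessment times: "Disease assessment will be performed at the end of cycle 4, cycle 8 and cycle 10".

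**The concern.** The plan gives two rules for counting responders, and they disagree for a patient whose early PD reverses only to stable disease. Two analysts working from the same data, one using the table and one using the sentence, could report different primary results.

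The count drives both decisions in 13.1: stop if 0 of the first 13 respond, and reject the regimen if 3 or fewer of 35 respond. With no CR or PR at all, four patients counted only through the sentence, at least one of them among the first 13, would pass both rules.

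The sentence also leaves open what non-confirmation means when there is no cycle-10 assessment. Section 9.4 ties confirmation to tolerating treatment. Under 6.5.1, treatment "will continue for at least 10 cycles (approximately 5 months) unless uncontrolled disease progression is observed", so it may end earlier. Patients with early PD are therefore among those likely to lack the confirming assessment. The 9.6 sentence has the same gap.

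**Working it through.** **1. The two rules applied to one patient.** Sum of diameters 50 mm at baseline, 62 mm at the end of cycle 4, 52 mm at the end of cycle 10.

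- Cycle 4: 62 − 50 = 12 mm, and 12/50 = +24%. Section 9.4 requires at least 20% and at least 5 mm, so this is PD.
- Cycle 10: 52 − 50 = 2 mm, and 2/50 = +4% from the smallest sum, so PD is not confirmed. PR needs a 30% fall from baseline, that is 0.70 × 50 = 35 mm or less. The patient has stable disease.
- 9.5 table and 13.1: not a responder. Sentence under the 9.5 table: responder.

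**2. Who is left unassigned when cycle 10 is missing.** Section 9.7.1 makes failures of deaths in the first 2 weeks owing to concurrent disease. Section 9.7.2 does the same for "Patients for whom there is inadequate information to judge tumor response because of loss of contact with our institution". Neither covers later deaths, or patients with early PD who stop before cycle 10 but remain in contact.

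**3. The plan's own operating characteristics.** Inputs from 13.1: first stage 13, stop at 0 responders; total 35 (13 + 22), reject at 3 or fewer; rates 5% and 20%. For a counted response rate p:

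- P(stop early) = (1 − p)^13
- P(promising) = Σ over x = 1 to 13 of C(13, x) p^x (1 − p)^(13−x) × P(Y ≥ max(0, 4 − x)), with Y binomial(22, p)
- Expected N = 13 + 22 × [1 − (1 − p)^13]

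| Quantity | Stated | Exact |
|---|---|---|
| P(promising) at 5% | 8.4% | 8.44% |
| P(promising) at 20% | 90% | 90.3% |
| P(stop early) at 5% | 51% | 51.3% |
| P(stop early) at 20% | 5% | 5.5% |
| Expected N at 5% | 23.7 | 23.71 |
| Expected N at 20% | 33.8 | 33.79 |

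For example, 0.95^13 = 0.5133, and 13 + 22 × 0.4867 = 23.71. The design is sound for whatever event is counted.

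**4. Effect of counting by the sentence.** Let q be the share of all patients who count only through the sentence. The counted rate is then (CR + PR) + q. The documents do not give q, so it is an assumed range. With a true CR + PR rate of 5%:

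| q (points) | Mean extra patients of 35 | Counted rate | P(promising) | P(stop early) | Expected N |
|---|---|---|---|---|---|
| 0 | 0 | 5% | 8.4% | 51% | 23.7 |
| 1 | 0.35 | 6% | 13.8% | 45% | 25.2 |
| 2 | 0.7 | 7% | 20.3% | 39% | 26.4 |
| 5 | 1.75 | 10% | 42.5% | 25% | 29.4 |
| 10 | 3.5 | 15% | 74.0% | 12% | 32.3 |

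At 1 point the error rate is already 13.8/8.44 = 1.6 times the stated one. With no true CR or PR and q = 10%, the counted rate is 10% and the regimen would still be called promising 42.5% of the time.

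**The case against.** The strongest reply is that the sentence should not be read alone. Section 9.5 opens by defining overall response through three types that all need CR or PR. Section 13.1, which holds the decision rules, repeats this and does not carry the disputed sentence. The melanoma experience in 9.4 and the PFS example point to a single intent: early PD should not bar a later response. On that reading the 8.4% stands. This is probably what was meant. But the example sits in the PFS definition and covers a patient who did reach PR, while the section that sets the response criteria states no such condition.

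Second, the percentages have no anchor in the documents. The 50% in 9.4 describes patients who became responders, and the phase 1 results in 4.4.3 say nothing about PD reverting to stable disease. That is correct, and the range is illustrative only.

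Third, non-confirmation at cycle 10 most naturally presupposes an assessment at that time, and calling a patient with uncontrolled progression a responder would be strained. This makes the missing-assessment gap secondary. It does not close it, because the plan assigns these patients no outcome.

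Finally, 13.1 reports that 8 patients had already been treated, so a change of wording must also settle how they are classified. That belongs in the fix and does not weaken the point.

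**Conclusion.** The contradiction is real and concerns the primary endpoint, so it must be fixed. It needs no assumption: the 50/62/52 mm patient is a non-responder by the table and a responder by the sentence.

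The stated 8.4% is not a miscalculation. It is the CR plus PR error rate only if the sentence is not used to add patients without CR or PR. If it is used, the error rate runs from 13.8% to 74.0% for an assumed 1 to 10 percentage points of such patients, at a true CR plus PR rate of 5%. The true share cannot be determined from the documents. The gap for missing cycle-10 assessments affects overall response and disease control alike.

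**What to change.** Replace the sentence under the 9.5 table with:

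> Measurable PD seen before the end of cycle 10 and not confirmed then does not by itself preclude overall response. The patient is a responder only if CR or PR as required by the table above is achieved. PD that reverses only to stable disease is not a response.

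Add to both 9.5 and 9.6:

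> A missing assessment is not non-confirmation. A patient with PD before the end of cycle 10 and no assessment at the end of cycle 10 is classified from the assessments that exist. The patient is a responder only if the CR or PR criteria of the 9.5 table were met, and has disease control only if the 9.6 table is satisfied without relying on absence of true PD at cycle 10.

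The second text also covers PD at cycle 4, stable disease at cycle 8 and nothing at cycle 10.

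The amendment should state that the same rule applies to patients already treated. The cost is wording only: no new visits, patients or data. Observed response and disease control rates may be less favourable, by an amount that depends on how many patients would otherwise have counted only through these sentences. With the change, the operating characteristics in 13.1 again describe CR plus PR.

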9.6. Criteria for Disease Control

Disease control definition among measurable and non-measurable disease combination

Controlled Disease	Non-measurable disease (i.e., bone)	Measurable disease (i.e., lung, liver, lymph nodes)
Type I measurable disease only	None	CR or PR, or SD \geq 4 months or no true PD (at cycle10)
Type II non-measurable disease only	CR, or SD \geq 4 M	None
Type III Both measurable and non-measurable disease	CR, or SD \geq 4 M	CR or PR, or SD \geq 4 months or no true PD (at cycle10)

A patient with PD of measurable disease prior to end of cycle 10 would be considered to have disease control if the PD is not confirmed at the end of cycle 10.

9.7. Response will not be considered evaluable in the following categories:

9.7.1. Early Deaths: Patients who die within the first 2 weeks of the initiation of drug therapy owing to concurrent disease. These cases will be considered treatment failures in the intent-to-treat analysis.

9.7.2. Lost to Follow-up: Patients for whom there is inadequate information to judge tumor response because of loss of contact with our institution (>2 months after a missed appointment) and with referring physician in spite of repeated attempts to locate them. These cases will be considered treatment failures in the intent-to-treat analysis.

9.7.3. Major Protocol Violation: Patients who significantly deviate from the treatment program by either adding or deleting another agent or another therapeutic maneuver or by modifying substantially the dosage and schedule of the drug under evaluation. Patients who do not fulfill the requirements outlined under Patient Eligibility are also included in this category.

9.8. Down staging is defined as a change in the tumor extent that results in reclassification of the primary tumor and/or regional lymph node metastases into a different (lower) T, N, or M subgroup.

9.9. All subjective toxic effects encountered during the study will be evaluated according to the CTCAE version 4.0. Objective toxic effects will be considered as the maximum numerical deviation from the normal range.

9.10. The survival of patients will be measured from the date of registration.

9.11. Patients will be monitored for 1 year after removal from the study or until death, whichever occurs first. Patients removed from study for unexpected adverse events will be monitored until AE is resolved or stabilized.

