6.5.2. Uncontrolled disease progression

Uncontrolled disease progression is defined as rapid growth of multiple measurable or non-measurable new lesions, or sum of the longest diameter of existing targeted lesions is >40% from the baseline.

Immunotherapeutic agents such as talimogene laherparepvec may produce antitumor effects by potentiating endogenous cancer-specific immune responses. The response patterns seen with such an approach may extend beyond the typical time course of responses seen with cytotoxic agents, and can manifest a clinical response after an initial increase in tumor burden or even the appearance of new lesions

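### Section 9.6 allows for early progression in measurable disease only, which for non-measurable disease contradicts 9.4 and the PFS rule in 13.1

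*Combined protocol and SAP*

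**What the plan says.** Section 9.4 defines PD by growth in the target lesions and adds that "the appearance of one or more new lesions is also considered progression", with no size limit. It then says, without restriction by type of disease, that true PD is confirmed at the end of cycle 10. The reason is that about half of the responders in the earlier melanoma study progressed before they responded. Section 6.5.2 gives the same reason: such agents "can manifest a clinical response after an initial increase in tumor burden or even the appearance of new lesions".

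Section 13.1 carries the rule into the analysis. For PFS, "this progression needs to be confirmed after the end of cycle 10", with no split by measurability. Its example scores progression at 2 months followed by PR at 5 months as PR. Its mixed-response rule judges both compartments at the same late time point: "progression of measurable disease and no progression of non-measurable disease at 5 months or vice versa" is uncontrolled disease.

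Sections 9.5 and 9.6 are narrower. The 9.5 note reads "A patient with PD of measurable disease prior to end of cycle 10 would be considered to have overall response" if that PD is not confirmed at cycle 10, and the 9.6 note reads "A patient with PD of measurable disease prior to end of cycle 10 would be considered to have disease control" on the same condition. The 9.6 table repeats the limit. Its measurable cells accept CR, PR, SD of at least 4 months, or absence of true PD at cycle 10. Its non-measurable cells, in the row for "Type II non-measurable disease only" and in the row for both kinds of disease, accept only CR or SD of at least 4 months.

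**The concern.** The delayed-confirmation rule is there because early worsening may not be real progression under this agent. Nothing in the stated rationale confines that to measurable lesions. Section 2.1.3 says that patients with only non-measurable local lesions will be enrolled, so the non-measurable column will be used.

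As written, the same course is scored differently according to whether the lesion can be measured, and two secondary endpoints can disagree about one patient: progression-free by 13.1, not controlled by 9.6. The disease control rate is then understated relative to the plan's own concept of true PD. An assessor has two defensible rules to choose from in an open single-arm trial, and may have to choose with results in view.

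**Working it through.** **Inputs.** Disease assessments fall at the ends of cycles 4, 8 and 10 (8.1.10), which 13.1 equates with 2, 4 and 5 months. The control cells are those of 9.6. The overall sample is 36 (5.0 and 13.1), of whom 35 belong to the two-stage design.

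**Step 1: one course, two kinds of lesion.** Patient A has non-measurable disease only and patient B measurable disease only. Each progresses at 2 months and is back to baseline, without CR or PR, at 5 months.

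| Rule | A (non-measurable) | B (measurable) |
|---|---|---|
| 9.4, true PD at cycle 10 | No | No |
| 13.1, PFS event at 2 months | No | No |
| 13.1, progression in either compartment at 5 months | No | No |
| 9.6, CR (or PR for B) | No | No |
| 9.6, SD of at least 4 months | No | No |
| 9.6, no true PD at cycle 10 | Not offered | Yes |
| 9.6 note | Does not apply | Applies |
| Disease control | **No** | **Yes** |

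The SD row is No because the recorded progression splits the period. At most 2 months precede it, and 5 − 2 = 3 months run from it to the cycle 10 assessment. Neither stretch reaches 4 months.

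**Step 2: both kinds of disease in one patient.** If the measurable part follows this course and the non-measurable part is stable for at least 4 months, both cells are met and disease is controlled. Exchange the two parts and the non-measurable cell fails, so disease is not controlled.

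**Step 3: size.** One patient changes the disease control rate by 1/36 = 2.8 percentage points (1/35 = 2.9). Two patients give 2/36 = 5.6 points and three give 3/36 = 8.3 points. The documents give no expected number, so one to three is an illustration and not an estimate.

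**Step 4: the primary endpoint.** Section 9.5 requires CR of non-measurable disease, so patient A is not a responder on any reading. The plan's design figures also reproduce. With b the binomial probability and X the number of responses among the 22 second-stage patients, P(promising) is the sum over x = 1 to 13 of b(x; 13, p) × P(X ≥ 4 − x). This gives 8.4% at p = 5% and 90.3% at p = 20%, against the stated 8.4% and 90%. Nothing here changes them.

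**The case against.** **The stricter non-measurable column may be intended.** Section 9.5 is also stricter there, and PFS and disease control are different endpoints that need not agree for every patient. This stands as a possible design choice. But the plan does not state it, and the confirmation rule in 9.4 is given for the study as a whole, in the same section that supplies the terms used in 9.6.

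**Section 9.4 could be read into the SD cell.** If unconfirmed PD is not PD, patient A was stable throughout and meets SD of at least 4 months. On that reading the extra alternative in the measurable column, and the note, would be largely redundant. Their presence suggests that SD was not meant to cover this case. At best there are two readings.

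**The wording of 9.4 has a limit.** Its definition describes target growth and new lesions, not worsening of existing non-measurable disease. That kind of progression is recognised in the mixed-response rule of 13.1, so the contradiction rests on 13.1 as well as on 9.4.

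**A stronger reading is tempting.** A reader might infer that early new nodules under 10 mm are never forgiven, that responders are therefore lost from the count set against 3/35, and that power falls. The documents do not support this:

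- The 9.5 note grants an allowance. It does not say that other early PD disqualifies a patient, so any exclusion is by omission only.
- The general rule in 9.4 and the example in 13.1 point to scoring early progression followed by PR as PR.
- No section assigns new lesions to a column by size, and nodules that disappear can meet the CR cell.
- A power loss would need an assumed share of non-measurable early progressions, and the melanoma figure of about 50% does not supply one.

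**Conclusion.** The inconsistency is real and lies in 9.6. For non-measurable disease that worsens early and is back to baseline without CR at cycle 10, the disease control definition departs from 9.4 and 13.1. Each such patient lowers the disease control rate by about 2.8 points relative to the scoring of the same course in measurable disease. This assumes a denominator of 36 and that recorded early progression interrupts SD. How often it will happen is unknown.

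The effect is confined to a secondary endpoint that carries no decision rule. In 9.5 the narrow wording is an ambiguity that 9.4 and 13.1 already lean towards resolving in the patient's favour. Loss of responders or of power should not be inferred from it.

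**What to change.** - In 9.6, add to the non-measurable cells of the Type II and Type III rows the cycle 10 alternative that the measurable column already has.
- In the notes under 9.5 and 9.6, replace the reference to measurable disease with PD of any kind: measurable, non-measurable or new lesion. In 9.5 this only removes the ambiguity; the response cells of the table must still be met.
- Base the judgement on the disease assessment already scheduled at the end of cycle 10, and give no credit to a patient who lacks one.
- Leave the 6.5.2 definition of uncontrolled progression unchanged.
- Settle the wording before responses are adjudicated.

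**Cost.** Two notes and two table cells change, with no added visit. The disease control rate becomes slightly more lenient for non-measurable disease. Imaging may also be missing. Under 8.1.9, CT or PET-CT is done as clinically indicated before cycle 5 and every 4 cycles after that, so before cycles 9 and 13 (5 + 4 and 9 + 4), and no scan is timed to the end of cycle 10. Some non-measurable sites may therefore have no image at that assessment, and the report should say how many credited patients are affected. If the stricter column is in fact intended, the alternative is to say so in 9.6 and to explain why it differs from 9.4 and 13.1.
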